## **7 CONCURRENT MEDICATIONS**

All subjects should be maintained on the same medications throughout the entire study period, as medically feasible, with no introduction of new chronic therapies.

### **7.1 Allowed Medications and Treatments**

Standard therapy is allowed. Patients on pain medication prior to procedure will be excluded, as stated above.

Prohibited Medications and Treatments: none

## 8 STUDY TREATMENTS

### 8.1 Method of Assigning Subjects to Treatment Groups

Prior to enrollment, the patients will be randomly assigned to cryoanalgesia or thoracic epidural groups in a 1:1 ratio using a computerized random sequence generator (<http://www.random.org/>). The values 1-20 are entered in the system, which creates a random sequence of the integers, formatted in 2 columns of 10 integers each. Column 1 is assigned to cryoanalgesia, and column two is assigned to thoracic epidural. The assignments are placed in closed envelopes with the integers on the outside of the envelopes. The study surgeons are blinded to the randomization. As patients are enrolled in the study, they are assigned an integer in order of enrollment (the first patient enrolled is patient 1, the next patient 2, etc.). The envelope associated with each patient number is opened on the morning of surgery, revealing their group assignment.

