STUDY DESIGN	This study is a prospective, randomized trial to compare cryoanalgesia to standard epidural analgesia for post-operative pain management in patients undergoing minimally invasive pectus excavatum repair (the Nuss procedure). 20 subjects will be randomized in 1:1 ratio to receive cryoanalgesia or epidural analgesia prior to their procedure.
PRIMARY OBJECTIVE	To compare post-operative length of stay in patients receiving cryoanalgesia vs. thoracic epidural analgesia for the Nuss procedure

SECONDARY OBJECTIVES	To compare post-operative pain scores, pain medication usage, side effects, and total cost of hospital stay in patients receiving cryoanalgesia vs. thoracic epidural analgesia for the Nuss procedure
NUMBER OF SUBJECTS	20
SUBJECT SELECTION CRITERIA	
Inclusion Criteria: Otherwise healthy male or female patients with pectus excavatum deformity, scheduled for Nuss procedure for chest wall correction, at least 13 years of age at time of Nuss procedure.
 
Exclusion Criteria:
 
 
• Age less than 13 years at time of surgery
 
• Pre-op pain medication usage
 
• Pectus carinatum
 
• Poland's syndrome or other complex chest wall anomaly
 
• Previous repair of Pectus Excavatum by any technique
 
• Previous thoracic surgery
 
• Congenital heart disease
 
• Bleeding dyscrasias
 
• History of previous problems with anesthesia or major anesthetic risk factors
 
• Pregnancy
 
• Non-English speaker
 

TEST PRODUCT, DOSE, AND ROUTE OF ADMINISTRATION	
AtriCure cryosurgical system (AtriCure, Inc., West Chester, Ohio)
 
The cryoprobe will be applied to the intercostal nerve under thoracoscopic visualization at the level of the incision and 2 interspaces above and below, bilaterally. The temperature and duration of cryoablation therapy is pre-set by the probe and cryosurgical system at 2 minutes to -60°C. Each nerve will receive one cycle of cryoablation.

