### 8.2 Blinding

Due to the nature of the study, it is not possible to blind patients or clinicians to the method of analgesia once the patient's group is revealed. However, to prevent selection bias, the study clinicians and patients will be blinded to the randomization process and selection until the time of surgery.

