## **10 EVALUATIONS BY VISIT**

### **10.1 Visit 1 – Pre-operative evaluation**

1. Review the study with the subject (subject's legal representative) and obtain written informed consent and HIPAA authorization and assent, if appropriate.
2. Record demographics data.
3. Record medical history, including a history of pectus excavatum and any prior treatments or procedures.
4. Record concomitant medications.
5. Perform a complete physical examination.
6. Perform and record vital signs.
7. Perform and record oximetry.
8. Perform and record results of blood pressure testing.
9. Assign unique study number for randomization

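### The single 10:10 list of 20 lets the last one or two allocations be deduced before the envelope is opened, so the blinding assurance in section 8.2 cannot hold for them

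*Combined protocol and SAP*

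**What the plan says.** The synopsis gives the target and ratio: "20 subjects will be randomized in 1:1 ratio to receive cryoanalgesia or epidural analgesia prior to their procedure". Section 8.1 gives the mechanism: "The values 1-20 are entered in the system, which creates a random sequence of the integers, formatted in 2 columns of 10 integers each". It then maps columns to arms: "Column 1 is assigned to cryoanalgesia, and column two is assigned to thoracic epidural". The list therefore holds exactly ten assignments per arm for exactly 20 patients.

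Numbers follow enrolment: "As patients are enrolled in the study, they are assigned an integer in order of enrollment". Section 10.1 places this step at Visit 1: "Assign unique study number for randomization". The reveal comes later: "The envelope associated with each patient number is opened on the morning of surgery, revealing their group assignment".

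Section 8.2 accepts that "it is not possible to blind patients or clinicians to the method of analgesia once the patient's group is revealed". It then states, as the safeguard against selection bias, that "the study clinicians and patients will be blinded to the randomization process and selection until the time of surgery".

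The synopsis names one site. Section 12.4 rules out replacing withdrawals. Neither section 8.1 nor 14.5 mentions concealed block sizes or a surplus of envelopes.

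**The concern.** In an open-label trial at one hospital, the team can keep a running count of the arms already revealed. The protocol itself publishes the total per arm. Once ten patients have had one method, every unopened envelope must hold the other. Before that point, the arm with more envelopes left is the better guess. Clinicians also cannot be blinded to a randomization process that their own protocol describes in full.

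What is at stake is selection. Some criteria in section 6.3 need judgement, such as those on anesthetic risk and complex chest wall anomalies. Section 12.3 lets the investigator withdraw a patient. Section 14.1 analyses only eligible randomized patients who receive the initial analgesic application and undergo the operation, so someone withdrawn before surgery leaves the analysis. With 10 patients per arm and an unblinded length-of-stay endpoint, one or two selective decisions could matter.

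**Working it through.** **The plan's own figure.** The documents state no figure for predictability. The stated sample size (section 14.5: difference 2 days, SD 1.3 days, two-sided 0.05, power 90%) reproduces: 2 × (1.960 + 1.282)² × 1.3² / 2² = 8.9, so 9 per arm and 18 in total. With 10 per arm, noncentral-t power is 90.2%, which is the reference value below.

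**Inputs.** 20 envelopes, 10 per arm, used in number order (section 8.1). All C(20,10) = 184,756 sequences are equally likely.

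**All earlier envelopes open.** The last k allocations are determined when they all fall in one arm:

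P(last k alike) = 2 × C(20 − k, 10) / C(20,10)

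| k | Probability |
|---|---|
| 1 | 100% |
| 2 | 47.4% |
| 3 | 21.1% |
| 4 | 8.7% |

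The sum over k = 1 to 10 is the expected number determined: 2 × C(20,11)/C(20,10) = 20/11 = 1.82 of 20.

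**Guessing.** Always naming the arm with more envelopes left gives 10 + (2²⁰/184,756 − 1)/2 = 12.3 correct of 20, against 10 by chance.

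**At enrolment, with envelopes pending.** The number is assigned at Visit 1 and the envelope opened at Visit 2. Let L be the number of earlier patients whose envelopes are still unopened when the next one enrols. The documents do not give the interval from enrolment to surgery, so L is an assumption. The synopsis plans 20 patients in 6 months, about one every 9 days. The expected number determined becomes the sum of the probabilities above from k = L + 1.

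| L | P(20th allocation determined) | Expected determined | Expected correct guesses |
|---|---|---|---|
| 0 | 100% | 1.82 | 12.3 |
| 1 | 47.4% | 0.82 | 11.8 |
| 2 | 21.1% | 0.34 | 11.6 |
| 3 | 8.7% | 0.13 | 11.4 |

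A patient who withdraws before the envelope is opened, if it then stays closed, has the same effect as one pending envelope.

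**A list of 24 (12 per arm), stopped at 20, with its length known.**
- Any allocation determined: 2 × C(12,7)/C(24,19) = 2 × 792/42,504 = 3.7%.
- Expected number determined: 0.057.
- Expected correct guesses: 11.45 of 20.
- Final split, from C(12,a) × C(12,20 − a)/C(24,20) with C(24,20) = 10,626: 10 v 10 in 4,356/10,626 = 41%; 11 v 9 in 5,280/10,626 = 50%; 12 v 8 in 990/10,626 = 9%.
- Noncentral-t power: 90.2%, 89.9% and 89.0% respectively.

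**The case against.** The design already has real protections: closed numbered envelopes, strict numbering by enrolment, surgeons kept from the list, and opening only on the day of operation. Even with every earlier envelope open, about 18 of 20 allocations are not determined. A single block of 20 also does far better than small blocks of known size. Blocks of four would give about 6.7 determined allocations and 14.2 correct guesses, against 1.8 and 12.3 here. All of this stands.

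A reader might infer that the last patients' arms are known before those patients enrol. The documents do not support that as a general statement. It requires every earlier patient to have had surgery first, and the gap between Visit 1 and surgery is not given. One pending envelope more than halves the expected number of determined allocations, and two cut it by about 80%. Because consent and eligibility are settled around enrolment, these lower figures are the relevant ones for them. The dropout that section 14.5 allows for works in the same direction.

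A reader might also infer a biased result. Nothing in the documents shows steering or lets its effect be estimated. As an illustration only, one patient whose stay differs by 3 days would move an arm mean by 3/10 = 0.3 day, or 15% of the planned 2-day effect. The 3 days is an assumption, equal to 2.3 of the plan's SDs, and it presumes that staff could foresee such a stay.

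Pending envelopes do not remove the point altogether. An allocation can still be deduced between enrolment and surgery, when withdrawal or rescheduling remains possible, and section 8.2 extends its assurance up to surgery.

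**Conclusion.** The point holds in a limited form. If all 20 patients are enrolled and all other envelopes have been opened, the final allocation is certain before its envelope is opened, and the last two or more are determined in 47% of lists. The assurance in section 8.2 therefore cannot hold for the final one or two patients. Its claim of blinding to the process also conflicts with section 8.1, which publishes that process.

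This weakens concealment at the end of the list. It does not mean that concealment is absent throughout. At enrolment the effect depends on the unstated number of pending surgeries, and it shrinks quickly as that number rises. The size of any bias is unknown. The change below is a cheap improvement to a stated safeguard; the point does not invalidate the design.

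**What to change.** In section 8.1, generate a longer list with the same tool, for example the values 1-24 in two columns of 12, and stop at 20 patients. Keep the list length, the column split and the unused envelopes from the study clinicians. This means moving those details out of the protocol text they receive and into a restricted document. Amend section 8.2 to claim only what the procedure then delivers. If the list stays at 20, section 8.2 should at least be reconciled with 8.1 by acknowledging that the final allocations can be deduced.

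**Gain.** Even if the length leaked, expected determined allocations fall from 1.82 to about 0.06, and the chance of any falls from 100% to about 4%. Better-than-chance guessing improves much less, from 12.3 to about 11.45 of 20.

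**Cost.** Four more envelopes and short edits to two sections. The arms end unequal in about 59% of lists, though the list itself remains 1:1. Under the plan's assumptions, power is 89.9% at 11 v 9 and 89.0% at 12 v 8, against 90.2% at 10 v 10.

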### 8.2 Blinding

Due to the nature of the study, it is not possible to blind patients or clinicians to the method of analgesia once the patient's group is revealed. However, to prevent selection bias, the study clinicians and patients will be blinded to the randomization process and selection until the time of surgery.

### 8.3 Test and Control Products

#### 8.3.1 Test Product

AtriCure cryosurgical system (AtriCure, Inc., West Chester, Ohio)

The cryoprobe will be applied to the intercostal nerve under thoracoscopic visualization at the level of the incision and 2 interspaces above and below, bilaterally. The temperature and duration of cryoablation therapy is pre-set by the probe and cryosurgical system at 2 minutes to -60°C. Each nerve will receive one cycle of cryoablation.

#### 8.3.2 Control Product

Thoracic epidural catheter will be placed by the pediatric anesthesia team prior to Nuss procedure. Catheters will be placed using sterile technique at approximately T5-6 or T6-7 interspaces; procedure specifics are dependent on the attending anesthesiologist's patient-dependent preference. Whether the patient will be awake or asleep for epidural placement will be at the discretion of the attending anesthesiologist. After placement, epidural infusion will begin with 0.1% ropivacaine and 2mcg/cc fentanyl. No bolus doses will be used.

### 8.4 Supply of Study Drugs and Equipment at the Site

All study drugs and equipment are regularly stocked in the hospital. Prior to each Nuss procedure, both the AtriCure Cryosurgical system and supplies for thoracic epidural will be made available in the operating room.

#### 8.4.1 Post-operative Pain Regimen

Please see separate post-operative pain regimen document

#### 8.4.2 Storage

Medication for epidural administration and post-operative pain regimen should be stored by the study site at controlled room temperature, 15 to 30°C (59 to 86°F). If the temperature of study drug

storage in the clinic/pharmacy exceeds or falls below this range, this should be reported to the Sponsor or study coordinator and captured as a deviation. All medications will be stored in the hospital pharmacy and dispensed by the patient's nurse. On discharge, subjects will be instructed to store the medication in original packaging at room temperature according to the instructions outlined on the Drug Administration Instructions.

## **8.5 Study Drug Accountability**

An accurate and current accounting of the dispensing and return of study drug for each subject will be maintained on an ongoing basis by a member of the study site staff. The number of study drug dispensed and returned by the subject will be recorded on the Investigational Drug Accountability Record. The study monitor will verify these documents throughout the course of the study.

## **8.6 Measures of Treatment Compliance**

Subjects will be asked to keep a patient diary noting the day and date they take their pain medications and any adverse events. They will be asked to bring their patient diary to each study visit along with all used and unused study drug containers.

# **9 STUDY PROCEDURES AND GUIDELINES**

A Schedule of Events representing the required testing procedures to be performed for the duration of the study is diagrammed in Appendix 1.

Prior to conducting any study-related activities, written informed consent and the Health Insurance Portability and Accountability Act (HIPAA) authorization must be signed and dated by the subject (if legally able to consent) or subject's parents or guardian(s). If appropriate, assent must also be obtained prior to conducting any study-related activities.

## **9.1 Clinical Assessments**

### **9.1.1 Concomitant Medications**

All concomitant medication and concurrent therapies will be documented at initial clinic visit/screening, during hospitalization, and at follow-up visits. Dose, route, unit frequency of administration, and indication for administration and dates of medication will be captured.

### **9.1.2 Demographics**

Demographic information (date of birth, gender, race) will be recorded at screening.

### **9.1.3 Medical History**

Past medical history and information regarding underlying diseases will be recorded at screening.

### **9.1.4 Physical Examination**

A complete physical examination will be performed by either the investigator or a subinvestigator who is a physician at the initial clinic visit. Qualified staff (MD, NP, RN, and PA) may complete the abbreviated physical exam at all other visits. New abnormal physical exam findings must be documented and will be followed by a physician or other qualified staff at the next scheduled visit.

### **9.1.5 Vital Signs**

Body temperature, blood pressure, pulse and respirations will be performed at all clinic visits and according to nursing unit protocol while patients are hospitalized.

### **9.1.6 Adverse Events**

Information regarding occurrence of adverse events will be captured throughout the study. Duration (start and stop dates), severity, outcome, treatment and relation to study drug will be recorded on the case report form (CRF).

## **10 EVALUATIONS BY VISIT**

### **10.1 Visit 1 – Pre-operative evaluation**

1. Review the study with the subject (subject's legal representative) and obtain written informed consent and HIPAA authorization and assent, if appropriate.
2. Record demographics data.
3. Record medical history, including a history of pectus excavatum and any prior treatments or procedures.
4. Record concomitant medications.
5. Perform a complete physical examination.
6. Perform and record vital signs.
7. Perform and record oximetry.
8. Perform and record results of blood pressure testing.
9. Assign unique study number for randomization

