## 1 BACKGROUND

Pectus excavatum is the most common congenital chest wall deformity, affecting approximately 1 out of every 1000 live births. It presents as a depression of the anterior chest wall, which can compress the heart and lungs, causing symptoms such as shortness of breath, exercise intolerance, and chest pain. The minimally invasive pectus excavatum repair, known as the Nuss procedure, is a common corrective procedure. It uses an implanted, thoracoscopically-guided convex metal bar to immediately reshape the chest wall. The benefits of this method compared to open repair include smaller incisions, no cartilage resection or osteotomy, and reduced operative times. However, the immediate reshaping of the chest wall results in significant post-operative pain, which can be challenging for patients, families, and clinicians. The ability to adequately control this post-operative pain is the primary determining factor for length of hospitalization following the procedure.

There is no standardized protocol for the management of pain following the Nuss procedure. Epidural analgesia and patient controlled analgesia (PCA) are the two most commonly used techniques, employed either independently or together. Thoracic epidural analgesia has been shown, with limited data, to be more effective than PCA alone for the first few postoperative days, but carries significant risks, including nerve damage, infection, and respiratory depression. Epidural analgesia also reduces post-operative mobility, and often necessitates the use of urinary catheters, which can increase risk of urinary tract infections. The use of epidural analgesia is limited to the first two to three post-operative days, at which time patients must be transitioned to alternate methods. This may increase length of stay, as it introduces an intermediate step prior to home oral regimen.

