#### **5.2 Secondary Efficacy Endpoints**

- Post-operative pain scores
- Post-operative pain medication usage
- Side effects
- Total cost of hospitalization

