### **10.2 Visit 2- Surgery and Post-operative hospitalization**

Time of Surgery

1. Urine pregnancy test (females)
2. Open randomization allocation envelope
3. Initial analgesic application (cryoanalgesia or epidural) and Nuss procedure

According to inpatient unit protocol

1. Perform and record vital signs.
2. Perform and record oximetry.

Once per day while inpatient

1. Concomitant medications review.
2. Perform abbreviated physical examination.

Twice-per-day study visits while inpatient

1. Record any Adverse Experiences
2. Administer inpatient survey (see separate document)

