#### **10.5 Visit 5- 3 months post-procedure**

1. Record any Adverse Experiences and Review subject diary for adverse experiences and dosing compliance.
2. Record changes to concomitant medications.
3. Perform abbreviated physical examination.
4. Perform and record vital signs.
5. Perform and record oximetry.
6. Perform post-op survey (see separate document for study tool).
7. Review pill bottles for medication usage.

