### 14.4 Analysis of Secondary Endpoints

Secondary outcomes include post-operative pain scores, pain medication usage, and side effects. Pain scores will be analyzed with Mann-Whitney rank sum tests (to compare between groups at each time point) and Wilcoxon signed-rank test (to compare scores within groups over time), with results considered statistically significant for  $p < 0.05$ . Pain medication usage between the two groups will be analyzed with two-tailed unpaired t test, again with results considered statistically significant for  $p < 0.05$ .

Adverse events will be tabulated by treatment group and will include the number of patients for whom the event occurred, the rate of occurrence, and the severity and relationship to study drug.

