## APPENDIX 1. SCHEDULE OF STUDY VISITS

	VISIT 1 pre-op	VISIT 2 procedure/hospit alization	VISIT 3 2 weeks post-op	VISIT 4 1 MONTH POST-OP	VISIT 5 3 MONTHS POST-OP	VISIT 6 1 YEAR POST-OP
Informed Consent	X					
Medical History	X					
Complete Physical Exam	X					
Abbreviated Physical Exam		X	X	X	X	X
Height	X	X				
Weight	X	X				
Vital Signs	X	X	X	X	X	X
Oximetry	X	X	X	X	X	X
Randomization	X					
Urine Pregnancy Test (females)		X				
Administration of Initial Analgesia (cryo vs. epidural)		X				
Survey Administration		X	X	X	X	X
Documentation of Pain Medication Usage		X	X	X	X	X
Counting of Returned Post-op Pain Medication			X	X	X	X
Initiate Subject Diary		X				
Subject Diary Review			X	X	X	X
Concomitant Medication Review	X	X	X	X	X	X
Adverse Experiences		X	X	X	X	X

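### No pain score is planned before surgery, so late pain cannot be read as change from the pre-operative state and chance imbalance at 10 per arm cannot be checked or adjusted

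*Combined protocol and SAP*

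**What the plan says.** Section 1 (Background) describes the deformity as "causing symptoms such as shortness of breath, exercise intolerance, and chest pain". Section 6.3 excludes patients who use pain medication before surgery, and Section 7.1 repeats it: "Patients on pain medication prior to procedure will be excluded, as stated above". No criterion excludes untreated chest pain.

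Section 10.1 lists nine items for Visit 1. The nearest to pain is "Record medical history, including a history of pectus excavatum and any prior treatments or procedures"; there is no survey and no pain score. Vital signs (Section 9.1.5) are temperature, blood pressure, pulse and respirations. The baseline variables in Section 14.2 do not include pain. In Appendix 1 the row "Survey Administration" has five marks for six visit columns, which I read as Visits 2 to 6.

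The first survey is the inpatient one in Section 10.2: "Administer inpatient survey (see separate document"). It falls under the twice-daily inpatient visits, not under the steps for the time of surgery. Sections 10.3 to 10.6 then schedule a survey at 2 weeks, 1 month, 3 months and 1 year, for example "Perform post-op survey (see separate document for study tool").

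The endpoint in Section 5.2 is "Post-operative pain scores", with no time points. Section 14.4 compares the arms at each time point by Mann-Whitney test and adds a "Wilcoxon signed-rank test (to compare scores within groups over time").

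**The concern.** Patients can arrive with differing amounts of chest pain from the condition being treated. Excluding users of pain medication removes treated pain, not all pain. Three things follow if nobody scores it.

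- **Within-arm change.** The first value in each series comes after surgery and after the assigned analgesic has been applied. The signed-rank tests can describe the course from that point. They cannot show whether a patient ends better or worse than before surgery.
- **Late pain in the individual.** Section 1 gives nerve damage as an epidural risk and cites animal data for axonal repair by about 4 to 6 weeks after freezing, so the 3-month and 1-year visits fall after expected recovery. Section 5.3 lists intractable pain as an adverse event to be related to the anesthetic method or the procedure. Without a prior score, new chest pain is hard to tell from chest pain that was always there.
- **Imbalance.** With 10 per arm and no stratification, the arms may differ by chance in pre-existing pain, and no score would exist to show it or correct for it.

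A pre-operative score cannot be recovered once surgery has taken place.

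**Working it through.** **The plan's own figure.** Section 14.5 gives SD 1.3 days, difference 2 days, two-sided alpha 0.05 and power 90%. By the normal approximation, n per arm = 2 × (1.960 + 1.282)² × 1.3² / 2² = 8.9, so 9 per arm and 18 in total, as stated. A t-based calculation gives 10 per arm, the planned enrolment. This rests on length of stay; no figure is given for pain scores, and nothing below changes it.

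**Inputs.** 10 per arm (Section 8.1). The correlation r between pre-operative and late pain is not in the documents. I assume 0.3 to 0.5 for the precision gain and look at 0 to 0.7 for validity.

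**Is the between-arm test still valid?** I simulated the planned exact Mann-Whitney test with normal scores, no true effect and 10,000 runs per correlation:

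| r | Type I error | Type I error given a baseline gap above 0.5 SD |
|---|---|---|
| 0 | 0.040 | 0.039 |
| 0.5 | 0.043 | 0.079 |
| 0.7 | 0.038 | 0.103 |

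The mean bias of the arm difference was within 0.004 SD of zero throughout. Overall the test holds its level. The last column describes the unlucky allocations, which the plan has no score to recognise.

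**How often is there a gap?** The SE of a chance difference in baseline means is √(2/10) = 0.447 SD. P(gap above 0.5 SD) = 2 × P(Z > 0.5/0.447) = 2 × P(Z > 1.118) = 0.26. P(gap above 1 SD) = 0.025.

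**How far does a gap move the late comparison?** The expected shift is r × gap. For a gap of 0.5 SD this is 0.15 SD at r = 0.3 and 0.25 SD at r = 0.5. The difference detectable with 80% power at 10 per arm is (1.960 + 0.842) × 0.447 = 1.25 SD, so the shift is 12% to 20% of it (0.15/1.25 and 0.25/1.25).

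**What would adjustment gain?** Adjusting for baseline multiplies the variance by 1 − r². Estimating the slope costs, on average for a normal covariate, a factor 1 + 1/(2n − 4) = 1 + 1/16 = 1.0625.

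- r = 0.3: 0.91 × 1.0625 = 0.967; equivalent gain 1/0.967 − 1 = 3%.
- r = 0.5: 0.75 × 1.0625 = 0.797; equivalent gain 1/0.797 − 1 = 25%.
- Break-even: (1 − r²) × 1.0625 = 1, so r = 0.24. Below that, adjustment costs a little precision.

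The detectable difference falls from 1.25 SD to 1.25 × √0.967 = 1.23 SD or 1.25 × √0.797 = 1.12 SD.

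**The case against.** A reader might infer that late pain scores cannot separate the treatment effect from pre-existing pain. For the comparison between arms the documents do not support that. Allocation is random, so pre-existing pain is balanced in expectation, and the planned test keeps its level without a baseline score. Nor do they support saying that every later score will look like improvement. That concerns within-arm change only, and the sound point is that its reference value comes after treatment.

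Other objections have weight:

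- The surveys are separate documents, and the pain endpoint names no time points. That pain is scored at Visits 3 to 6 is a reasonable inference, not a stated fact. The survey might also ask about pain before surgery.
- The medication exclusion, and the synopsis requirement that patients be otherwise healthy, narrow the range of pre-existing pain. Many baseline scores may be near zero, which would weaken both the correlation and any rank-based adjustment.
- The medical history may note chest pain, so an imbalance is not wholly invisible. A history note is still not a score that can be compared or adjusted for.
- Lasting nerve injury is mainly a safety question, and adverse events are collected to 1 year with severity and relationship. That remains true, but relating late pain to the anesthetic method would be easier with a prior score.
- The point touches late values of one secondary endpoint. For inpatient scores a pre-operative value would probably add little.

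These objections limit the size of the point. They do not supply the missing pre-operative reference.

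**Conclusion.** The point holds as a cheap improvement, not as a flaw that invalidates a planned analysis. No pre-operative pain score is scheduled, although the protocol itself names chest pain as a symptom and screens out only medicated patients. The clearest loss is in the within-arm comparison, which has no pre-treatment reference; randomisation does not help there. The second loss is that a baseline gap above 0.5 SD, with a chance of about 26% at 10 per arm, can be neither checked with a score nor adjusted for. Precision is the weakest argument: 3% to 25% in equivalent sample size, resting on assumed correlations of 0.3 to 0.5 and a roughly normal baseline score, and less if many scores sit near zero. All of this as it bears on late pain depends on the survey scoring pain at Visits 3 to 6. The between-arm Mann-Whitney test, the primary endpoint and the sample size stand as they are.

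**What to change.** - Add the survey's pain items to Section 10.1 and mark them in the Visit 1 column of Appendix 1; list the score among the baseline variables in Section 14.2. Section 8.1 keeps the allocation concealed until the morning of surgery, so the Visit 1 score would be given without knowledge of the arm.
- State in Section 14.4, or in the SAP that Section 14 promises, whether the survey scores pain at Visits 3 to 6. If it does, use the Visit 1 score as the reference for within-arm change at those visits and report the number in each arm whose pain is worse than before surgery.
- Keep the Mann-Whitney test as planned. Beside it, add one baseline-adjusted comparison of the arms for Visits 3 to 6 (for example, analysis of covariance on ranks), labelled supportive. Say in advance what will be done if most baseline scores are tied at the floor.

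The cost is one short questionnaire at an existing visit and one degree of freedom in a supportive analysis. It needs no extra visit or procedure and no change to treatment or enrolment.
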